## 2. Glossary

Term	Definition
ADE	Adverse device effect: Adverse event related to the use of an investigational medical device. Note: This definition includes adverse events resulting from insufficient or inadequate instructions for use, deployment, implantation, installation, or operation or any malfunction of the investigational medical device. Note: This definition includes any event resulting from use error or from intentional misuse of the investigational medical device. See Clinical Event definition for more information.
AE	Adverse event: Any untoward medical occurrence, unintended disease or injury, or untoward clinical signs (including abnormal laboratory findings) in subjects, users or other persons, whether or not related to the investigational medical device. Note: This definition includes events related to the investigational medical device or the comparator. Note: This definition includes events related to the procedures involved. Note: for users or other persons, this definition is restricted to events related to investigational medical devices. See Clinical Event definition for more information.
Assent	An agreement by an individual not competent to legally give valid informed consent generally because of age or mental status
CIP	Clinical Investigation Plan Document that state(s) the rationale, objectives, design and proposed analysis, methodology, monitoring, conduct and recordkeeping of the clinical investigation.  Note: The term "protocol" is synonymous with "CIP". However, protocol has many different meanings, some not related to clinical investigation, and these can differ from country to country. Therefore, the term CIP is used in this International Standard.
EC	Ethics Committee: Independent body whose responsibility is to review clinical investigations in order to protect the rights, safety and well-being of human subjects participating in a clinical investigation. Also known as the Institutional Review Board (IRB).  Note: For the purposes of this International Standard, "ethics committee" is synonymous with "research ethics committee," "independent ethics committee" or "institutional review board".  The regulatory requirements pertaining to ethics committees or similar institutions vary by country or region.
eCRF/CRF	(Electronic) Case Report Form: A paper or electronic data collection form, designed to collect information on each subject as required by the Study Protocol /Clinical Investigation Plan.
ENT	Ear, nose and throat, a subspecialty of medicine dealing with the diagnosis and management of medical conditions related to the ears, nose, and throat, also referred to as otolaryngology or otorhinolaryngology
FLACC behavioral pain assessment scale	Face, Legs, Activity, Cry, Consolability behavioral pain assessment scale:  A validated pain measurement instrument to assess pain for children age 2 months to seven (7) years of age. The scale has five (5) criteria with 0 representing behavior with no pain and 2 representing the most pain.
GCP	Good Clinical Practice:  A standard for the design, conduct, performance, monitoring, auditing, recording, analyses, and reporting of clinical studies that provides assurance that the data and reported results are credible and accurate, and that the rights, integrity, and confidentiality of study subjects are protected.
Hemostasis	The arrest of bleeding, whether it be by normal vasoconstriction (the vessel walls closing temporarily), by an abnormal obstruction (such as a plaque) or by coagulation or surgical means (such as ligation).
Intra-operative Bleeding	Bleeding that occurs during the course of the surgical operation.

MDT17024BZP

Version 5.0 (18 MAR 2019)

Page 7 of 47

Medtronic

Term	Definition
IRB	Institutional Review Board: Any board, committee, or other group formally designated by an institution to review, to approve the initiation of, and to conduct periodic review of, biomedical research involving human subjects. The primary purpose of such review is to assure the protection of the rights and welfare of the human subjects. Also known as Ethics Committee (EC).
LAR	Legally Authorized Representative: Individual or judicial or other body authorized under applicable law to consent, on behalf of a prospective subject, to the subject's participation in the clinical investigation. LAR may be the subject's parent or parental guardian. For the purposes of this protocol LAR will be used, but may be synonymous with parent in cases where a parent is the LAR.
Likert Scale	A psychological measurement device that is used to gauge attitudes, values, and opinions, generally using a 5-point rating system.
Peritonsillar abscess	A formation of pus within the peritonsillar space (beside the tonsil) generally formed as the result of bacterial infection within the loose connective tissue found in the area.
SAE	Serious Adverse Event: Adverse event that: a) Led to a death, b) Led to a serious deterioration in the health of the subject, that either resulted in: 1) Resulted in a life-threatening illness or injury, or 2) Resulted in a permanent impairment of a body structure or a body function, or 3) In-patient or prolonged hospitalization, or 4) Medical or surgical intervention to prevent life threatening illness or injury or permanent impairment to a body structure or a body function, or Led to fetal distress, fetal death or a congenital abnormality or birth defect.  Note: Planned hospitalization for a pre-existing condition, or a procedure required by the CIP, without serious deterioration in health, is not considered a serious adverse event.
SADE	Serious Adverse Device Effect:  Adverse device effect that has resulted in any of the consequences characteristic of a serious adverse event.
Tonsillectomy	A surgical procedure to remove the tonsils
US	United States
USADE	Unanticipated Serious Adverse Device Effect:  Any serious adverse effect on health or safety or any life-threatening problem or death caused by, or associated with, a device, if that effect, problem, or death was not previously identified in nature, severity, or degree of incidence in the CIP or application (including a supplementary plan or application), or any other unanticipated serious problem associated with a device that relates to the rights, safety or welfare of subjects.
Wong-Baker FACES® Scale	An illustrated pain scale ranging from a happy face at 0 "No Hurt" to a crying face at 10 "Hurts Worst"

MDT17024BZP Version 5.0 (18 MAR 2019) Page 8 of 47

e 8 of 47 Medtronic

3. Synopsis		
Title	A prospective, multi-center, single arm study of BiZact TM on children	
	undergoing tonsillectomy	
Clinical Study Type	Pre-market Pivotal / IDE Study	
Product Name	BiZact ™ (BZ4212)	
Sponsor	Medtronic, Minimally Invasive Therapies Group, Surgical Innovations	
Local Sponsors	Covidien-Medtronic	
	Minimally Invasive Therapies Group	
	Surgical Innovations	
	[name]	
	[name]	
	Covidien-Medtronic	
Indication under	Tonsillectomy in children (age 2-12 at the time of the procedure,	
investigation	inclusive)	
Investigation Purpose	The purpose of this study is to assess safety and performance with	
	the use of the BiZact ™ device in tonsillectomy procedures in	
	children.	
Product Status	Food and Drug Administration (FDA) cleared for adult ENT	
	procedures including tonsillectomy	
	Therapeutic Goods Administration (TGA) License for ENT	
	procedures including tonsillectomy in adults, children and	
	adolescents.	
Primary Objective(s)	The primary objective of this study is to assess safety and	
	performance with the use of the BiZact™ device in children (ages 2-	
	12 at the time of the procedure, inclusive) tonsillectomy procedures.	
Study Design	A prospective, multi-center, single arm, study of BiZact™ on children	
	undergoing tonsillectomy.	
Primary Endpoint(s)	Intra-operative blood loss: The study will be considered a success if	
	the mean intra-operative blood loss is less than the mean intra-	
	operative blood loss associated with conventional tonsillectomy in a	
	large meta-analysis (Alexiou et al. 2011). See the Statistics section	
	below for more details.	

MDT17024BZP Version 5.0 (18 MAR 2019) Page 9 of 47

Medtronic

Secondary Endpoint(s)	Study will analyze and describe device performance and patient		
	response related to the following:		
	
 
Ability to dissect tonsils with investigational medical device
 
		
	via Likert Scale (Very Good, Good, Acceptable, Poor, Very		
	Poor)		
	
 
Usability Challenges
 
		
	
 
Ability to achieve hemostasis (arrest of bleeding, as
 
		
	assessed by visual inspection of the Investigator) without		
	the use of other interventions (e.g. energy device or		
	sutures)		
	
 
Evaluation of post-operative pain incidence and severity
 
		
	measured using the Wong-Baker FACES® Pain Rating Scale		
	and FLACC behavioral pain assessment scale		
	
 
Analgesic consumption (standard of care) and concomitant
 
		
	medications (via patient diary)		
Sample Size	A minimum of sixty (60) completed procedures, with at least 40%		
	study wide in the age range of 2-5 years of age, will be undertaken at		
	a minimum of 2 sites in US. When 36 procedures with subjects ≥6		
	years of age have been completed (60% of total minimum		
	enrollment), enrollment for this age group will close.		
	Power considerations are detailed in the Statistics section below.		
Inclusion/Exclusion Criteria	Inclusion Criteria:		
	1. Children subjects 2-12 years of age at time of procedure,		
	inclusive		
	Scheduled to undergo tonsillectomy		
	3. The subject and subject's Legally Authorized Representative		
	(LAR) is willing to participate and consents to participate, as		
	documented by signed informed consent form and/ or assent		
	form (as applicable)		
	Exclusion Criteria:		

		•		
MDT17024BZP	Ve	ersion 5.0 (18 MAR 2019)	Page 10 of 47	Medtronic
	3. 4. 5.	visits Female subjects pregnant The subject has comorbidi Investigator, will not be ap subject has an estimated li months. The subject is participating	isorders sillar abscess ders (Trisomy 21) se (including but r ailure, left-sided r ailure, coronary a nic heart failure, a se with the required at time of proced ties which, in the opropriate for the ife expectancy of	neart failure, rtery disease, rcute heart  d study follow-up ure opinion of the study or the less than 6  ed in any drug or
Study Procedures and Assessments	device research study within 30 days of enrollment.  Pre-operative & Operative Assessments:  Demographics Histories: Medical, Surgical, Medication Urine pregnancy test for females of child bearing potential Type of admission AE/SAE Assessment Pre-operative physical exam (abbreviated) Intra-operative bleeding volume (excluding other fluids) Operative field irrigant volume Presence of gastric fluids Volume of stomach juices and blood in suction container Differential weight of any sponges applied to tonsil bed to absorb blood Surgical performance parameters Operative time - time from the first incision to complete hemostasis (arrest of bleeding as assessed by visual inspection of the Investigator) of the tonsillar bed (excluding time for closing)			

BiZact™ Pediatric	Clinical Study Protocol	
MDT17024BZP	Version F. 0 (18 MAR 2010) Page 11 of 47	edtronic
WIDTITOZADZI	
 
Device ease of use
 
Usability challenges
 
Alternate device(s) use (if any)
 
Ability to dissect tonsil with device graded via Likeri (Very Good, Good, Acceptable, Poor, Very Poor)
 
Tonsil size measurement (mL)
 
Concomitant Medications
 
Device accountability
 
Follow-up Assessments (Forms filled out by subject or parent/L post-operative days 1-7, 10, 14 and 28 see full protocol for assessment windows):
 
Pain level
 
Analgesic consumption
 
Ability to return to normal diet (via Patient Diary)
 
Ability to return to normal activity (via Patient Diary)
 
Incidence of post-operative hemorrhage - any primary (hours) requiring medical intervention and secondary (> hours) bleeding requiring medical intervention (e.g., car admission for observation, or re-operation)
 
	t Scale AR on (≤24 24
Safety Assessments	
 
Incidence of post-operative readmission
 
Safety will be assessed as the proportion of subjects with:         
 
Post-operative hemorrhage - any primary (≤24 hours) required medical intervention and/or secondary (>24 hours) bleeding requiring medical intervention (e.g., cautery, admission for observation, or re-operation)
 
Post-operative readmission
 
Evidence of glossopharyngeal nerve damage (e.g., prolonged pain or difficulty swallowing) as diagnosed by the surgeon
 
Other intra/post-operative complications (complications reto device deficiencies)
 
Other adverse events (e.g., post-operative dehydration, feweste.)
 
Localized Infection

	g ed lated er,

MDT17024BZP Version 5.0 (18 MAR 2019) Page 12 of 47

Medtronic

#### **Statistics**

The analysis technique will be a 1-sample t-test (or Wilcoxon ranked sign if nonparametric test is desired), with a one-sided type I error rate ( $\alpha$ ) of 0.025. A sample size of 60 is selected to ensure that multiple surgeons participate and to create an opportunity for a range of subject ages to be enrolled. Statistical power for a sample size of 60 exceeds 99%.

The primary hypotheses of this study are:

H0: Mean intra-operative blood loss = 31 mL HA: Mean intra-operative blood loss < 31 mL

The performance goal of 31 mL derives from a meta-analysis comparing modern technology to conventional techniques (i.e. electrocautery and cold steel) (Alexiou *et al.* 2011). This paper included a total of 3139 patients included in thirty-three published studies. The values from all of the studies that reported intra-operative bleeding were combined to calculate a mean blood loss. This value encompasses a variety of techniques and technologies and a number of different studies to capture a realistic value for comparison.

Intraoperative blood loss during tonsillectomy with BiZact™ is expected to be low. The expected mean value for the BiZact™ device is a conservative estimate derived from data for LigaSure™ and other vessel sealing systems in the Alexiou meta-analysis. The expected standard deviation is the average of the standard deviation values for all studies that reported blood loss in the meta-analysis.

Expected mean for BiZact™: 10 mL Expected standard deviation: 15.1 mL

Additionally, descriptive statistics for blood loss will be reported for different age groups (ages 2-5 and ages 6-12) as well as for different sites, surgeons, and countries.

Secondary endpoints will be evaluated with descriptive statistics. For continuous variables, the mean, median, and standard deviation will be reported, along with a 95% confidence interval for the mean where appropriate.

For categorical data, proportions will be reported, along with 95% confidence intervals where appropriate.

MDT17024BZP Version 5.0 (18 MAR 2019)

Page 13 of 47

Medtronic

#### 4. Introduction

#### 4.1. Background

#### 4.1.1. Tonsillectomy Procedure

Tonsillectomy is one of the most frequently performed otorhinolaryngologic procedures. Aside from the conventional technique of cold steel and electrocautery dissection, the introduction of numerous energy based tools and techniques allows for the simultaneous dissection and sealing of vessels, potentially improving safety and reducing the complications of the procedure (1-3). Generally thought of as safe and effective, energy based devices such as laser, Shaw scalpel, electrosurgical devices (needle, scissor, or knife), radiofrequency needle ablation device, thermal welding, and Coblator™, use heat energy to denature protein, leading to vascular tamponade and hemostasis (arrest of bleeding). Unfortunately, a byproduct of using this energy during surgery is the lateral heating of the surgical area, which can damage adjacent structures, delay wound healing, increase post-operative pain, and increase the subject's time to return to normal diet and activity (4).

In order to address these concerns, Medtronic has developed BiZact™, a bipolar electrosurgical instrument intended for use in open surgical procedures, such as tonsillectomies, where ligation and division of vessels, tissue bundles, and lymphatics is desired. BiZact™ is designed as a pistol grip radiofrequency (RF) sealer/dissector for use with vessels up to and including 3mm. Compatible with the already in use Valleylab™ (LS10, FT10, ForceTriad™) energy platforms, BiZact™ employs bipolar electrosurgical RF energy and pressure to ligate vessels interposed between its jaws which can then be transected using the built-in knife deployed by the device trigger. Based off of Ligasure™ technology, bipolar electrosurgical devices have demonstrated utility for tonsillectomy procedures, providing hemostasis while minimizing postoperative pain (5, 6, 8, 9).

#### 4.1.2. BiZact™ Device

Animal model studies have found BiZact™ to be able to achieve hemostasis and minimize lateral thermal spread potentially resulting in reduced post-operative pain. Details of preclinical testing can be found within the BiZact™ instructions for use (IFU) and in the Investigator's Brochure. Additionally, the performance of the BiZact™ device is also being evaluated in an adult tonsillectomy pilot study in the US and Europe (ClinicalTrials.gov Identifier: NCT02876575).

#### 4.2. Purpose

The purpose of this study is to assess safety and performance of the BiZact™ device in tonsillectomy procedures in children. Sixty (60) pediatric subjects (ages 2-12 inclusive) will be treated for tonsillectomy with BiZact™ enrolled at a minimum of 2 clinical sites across the USA with enrollment and completion of the tonsillectomy procedure with the study device not to exceed 36 subjects per site. The study will be considered a success if the mean intra-operative blood loss is less than the mean intra-operative blood loss associated with conventional tonsillectomy in a large meta-analysis (7). At the conclusion of the study, data will be submitted to the FDA for consideration for a pediatric indication and for publication.

MDT17024BZP

Version 5.0 (18 MAR 2019)

Page 14 of 47

Medtronic

#### 5. Objectives and Endpoints

#### 5.1. Objectives

#### 5.1.1. Primary Objective

The primary objective of this study is to assess safety and performance with the use of the BiZact™ device in children (ages 2-12 at the time of the procedure, inclusive) tonsillectomy procedures.

#### 5.2. Endpoints

#### 5.2.1. Primary Endpoint

The primary endpoint of this study is the amount of intra-operative blood loss. The study will be considered a success if the mean intra-operative blood loss is less than the mean intra-operative blood loss associated with conventional tonsillectomy in a large meta-analysis (7). See the Statistical Design and Methods (Section 13) for additional details.

#### 5.2.2. Secondary Endpoints

- Ability to dissect tonsils with investigational medical device (Likert Scale: Very Good, Good, Acceptable, Poor, Very Poor) and Usability Challenges
- Ability to achieve hemostasis (arrest of bleeding, as assessed by visual inspection of the investigator) without the use of other methods (e.g. energy device or sutures)
- Evaluation of post-operative pain incidence and severity measured using the Wong-Baker FACES® Pain Rating Scale or FLACC behavioral pain assessment scale
- Analgesic consumption (standard of care) and concomitant medications (via Patient Diary)

#### 5.2.3. Safety Assessment

The study will assess the observed rates of device-related adverse events. This includes, but is not limited to consideration of the following conditions:

- Post-operative hemorrhage
  - Any primary (≤24 hours) requiring medical intervention and/or secondary (>24 hours) bleeding requiring medical intervention (e.g., cautery, admission for observation, or reoperation)
- Post-operative readmission
- Evidence of glossopharyngeal nerve damage as diagnosed by the investigator via subject assessment
- Other intra/post-operative complications (complications related to device deficiencies)
- Other adverse events (e.g., post-operative dehydration, fever, etc.)
- Localized Infection
  - o Infection confined to a single organ or tissue

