#### 9.7. Assessment of Safety

Safety will be assessed by monitoring the occurrence of adverse events (AEs), serious adverse events (SAEs), death, adverse device effects (ADE), unanticipated serious adverse device effects (USADE), device deficiencies or the presence of localized infection as defined in Section 10. Assessments will take place starting during the procedure as soon as the device is in contact with the subject, through post-operative day 28 (+7) and will be recorded in the eCRF.

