All AEs observed during the course of this study, regardless of severity or relationship to the device will be recorded on the appropriate eCRF. Adverse events regardless of relatedness will be treated per standard of care at each institution. For example, the management of pain or bleeding will be at the discretion of the treating physician, as he or she is monitoring the patient's condition.

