#### 11.1.3. Adverse Device Effect (ADE)

In alignment with ISO 14155:2011 (Section 3.1), an Adverse Device Effect is an adverse event related to the use of an investigational medical device.

This definition includes adverse events resulting from insufficient or inadequate instructions for use, deployment, implantation, installation, or operation, or any malfunction of the investigational medical device.

This definition includes any event resulting from use error or from intentional misuse of the investigational medical device.

Adverse Device Effects will be reported by the Investigator(s). If escalation is required (due to the potential need for reporting) ADEs will be reviewed by Medtronic Medical Affairs. Both confirmed and

MDT17024BZP

Version 5.0 (18 MAR 2019)

Page 32 of 47

possible device related events will be included in the study report. ADE(s) may be anticipated or unanticipated (UADE).

Examples of adverse device effects include but are not limited to: unintended cutting, unintended electrical path, or arcing.

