#### 11.3. Adverse Event Recording

All observed adverse events (ADEs, UADEs and SAEs) will be collected and documented at the time of surgery to 28 (+7) days follow-up. If the adverse event is recorded at the last subject visit and considered serious and device-related, the event should be followed for resolution for up to seven (7) days, or until the resolution of the event, whichever is earliest, even if this falls outside the 28 (+7) day visit window. To ensure consistency of data collection no new events will be recorded after the 28 (+7) day visit window, even if the subject is being followed for resolution of another event. If the adverse event is ongoing at the end of the study, and exceeds the follow up time frame, the patient will continue to receive standard care with their normal physician, and the event will be listed as ongoing.

Assessment of the occurrence of an AE will be based on changes in the subject's physical examination, laboratory results and/or signs and symptoms. Adverse events will be monitored until a subject completes the study unless the Investigator determines the event is related to the device, in which case they will be monitored until resolution if possible. Medical care will be provided, as defined in the informed consent, for any AE related to study participation. Adverse events will be collected on an AE eCRF and applicable source documentation. To the extent possible, the event to be recorded and reported is the event diagnosis as opposed to event symptoms (e.g., fever, chills, nausea and vomiting in the presence of a clinically diagnosed infection is to be reported as infection only). For the purposes of this protocol, only those AEs occurring after enrollment and the commencement of the tonsillectomy with the study device will be recorded.

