## 13.5. Statistical Analysis of Safety Endpoints

The safety endpoints will be analyzed using the ITT population. Proportions of the following events will be reported for the study:

Post-operative hemorrhage

MDT17024BZP

Version 5.0 (18 MAR 2019)

Page 39 of 47

Medtronic

- Any primary (≤24 hours) requiring medical intervention and/or secondary (>24 hours) bleeding requiring medical intervention (e.g., cautery, admission for observation, or reoperation)
- Post-operative readmission
- Evidence of glossopharyngeal nerve damage as diagnosed by the investigator via subject assessment (e.g., prolonged pain or difficulty swallowing)
- Localized Infection
  - o Infection confined to a single organ or tissue
- Other serious device-related adverse events

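### The three safety lists disagree, and Section 13.5 plans no proportion for other adverse events that are non-serious or judged unrelated to the device

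*Combined protocol and SAP*

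**What the plan says.** Three places define the safety summary.

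- **Synopsis, Safety Assessments.** "Safety will be assessed as the proportion of subjects with" each of six listed items. No general relatedness condition is attached; one item, complications, is limited by its own wording to those tied to device deficiencies.
- **Section 5.2.3.** The same six items, introduced by "The study will assess the observed rates of device-related adverse events". The list is described as not exhaustive. It includes "Other adverse events (e.g., post-operative dehydration, fever, etc".
- **Section 13.5.** Proportions in the ITT population for five items. Four carry over from the earlier lists with no stated relatedness condition. The fifth is "Other serious device-related adverse events".

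Sections on assessment and recording bear on these lists. Section 9.7 bases safety on the occurrence of adverse events generally, as well as serious events, deaths and device effects. Section 11.1.1 states: "All AEs observed during the course of this study, regardless of severity or relationship to the device will be recorded on the appropriate eCRF". Section 11.1.3 adds that confirmed as well as "possible device related events will be included in the study report".

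**The concern.** Safety is part of the primary objective (Section 5.1.1), and the data are to go to the FDA for a pediatric indication (Section 4.2). The study has no comparator (Section 6.2), so causality cannot be read from a difference between groups. The most transparent display is therefore the proportion of children with each event whatever its cause, with the device-related subset beside it.

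The three lists do not settle whether that display will be produced. The 5.2.3 lead-in, taken literally, filters every item by relatedness. Section 13.5 does not filter the four main events, but it narrows the residual category to events that are both serious and device-related. Two kinds of recorded event then lose the proportion that the synopsis plans: non-serious device-related events, and other adverse events judged unrelated. If the choice of list is left open, it would be made after open-label data have been seen.

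**Working it through.** The check is a comparison of texts. The plan states no figure here to reproduce.

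**Step 1: the lists side by side**

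| Item | Synopsis | 5.2.3 | 13.5 |
|---|---|---|---|
| Post-operative hemorrhage | listed | listed | listed |
| Readmission | listed | listed | listed |
| Glossopharyngeal nerve damage | listed | listed | listed |
| Localized infection | listed | listed | listed |
| Complications of device deficiencies | listed | listed | no row |
| Other adverse events | listed | listed | no row |
| Other events, serious and device-related | not separate | not separate | listed |
| Relatedness wording in the lead-in | none | device-related | none |
| Unit | proportion of subjects | observed rates | proportions of events |

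The counts are 6, 6 and 5, with four items common to all three. In 13.5, 6 − 4 = 2 items are dropped and one narrower row is added: 4 + 1 = 5.

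**Step 2: kinds of event traced through the lists**

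- *Serious, device-related event outside the four:* within scope of all three lists.
- *Non-serious device-related event outside the four, for example a minor thermal burn:* within other adverse events in the synopsis and consistent with the 5.2.3 lead-in, but no row in 13.5. Section 11.1.3 promises that it appears in the study report, not that a proportion is given.
- *Other event judged unrelated, for example dehydration without readmission:* counted under the synopsis. In 5.2.3 the list item admits it and the lead-in excludes it. There is no row in 13.5, whether or not it is serious.
- *Hemorrhage or readmission judged unrelated:* counted under the synopsis and 13.5; excluded only by a literal reading of the 5.2.3 lead-in.

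**Step 3: whether another rule closes the gap**

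- Section 11.1.1 exempts certain transient nausea and emesis, constipation and expected pain from reporting. Dehydration and fever are not on that list, so they are recorded.
- Section 11.3 gives as its example that "fever, chills, nausea and vomiting in the presence of a clinically diagnosed infection is to be reported as infection only". Fever with a localized infection therefore reaches 13.5 through the infection row, and dehydration that leads to readmission through the readmission row. The rest has no row.
- Section 13.1 supplies a general format (frequencies and percentages) and Section 15.2 supplies MedDRA coding. Neither fixes the list or a relatedness rule.

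No reading of 5.2.3 brings it into line with 13.5. Read broadly, it includes other events that 13.5 omits. Read narrowly, it still includes non-serious device-related events, which 13.5 also omits.

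**The case against.** The strongest reply is that this is a wording mismatch with little consequence. Section 13.5 is the analysis section, and it counts the four main events whatever their cause. All adverse events are recorded and coded, Section 13.1 would summarize them as frequencies and percentages, and 13.5 does not say that its list is exclusive. Section 11.1.3 already commits device-related events to the report without a seriousness limit. Dehydration and fever are only examples of a catch-all, and Section 10.1.1 names them as risks of standard tonsillectomy, not among the device risks, so narrowing the residual row could be deliberate. Section 13.8 refers to a SAP for full details, and no separate SAP text is in the document reviewed.

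Much of this stands. No data are lost, and the residual events may well be tabulated somewhere. What does not follow is that the contradiction is resolved: none of these sections sets a relatedness rule or restores the two proportions. A SAP could settle the analysis, but the three protocol sections would still disagree.

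A reader might infer that hemorrhage and readmission will be reported only when rated device-related, so that their rates would fall. The documents do not support that. Section 13.5 attaches no relatedness condition to them, and treating the word other in its last row as a filter on the four rows above is strained. The 5.2.3 lead-in also fits poorly with items in its own list, such as readmission.

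**Conclusion.** The contradiction is real and confined to descriptive safety reporting. Section 13.5 keeps 4 of the 6 items planned in the synopsis and 5.2.3, and puts one narrower row in place of the other 2. Followed as written, it plans no proportion for non-serious device-related events outside the four items, or for other adverse events judged unrelated.

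No numerical effect can be given, because the documents state no event rates. The conclusion rests on the sections as worded and assumes that no separate SAP supplies the missing rows. The primary blood-loss test, its alpha, the power and the success rule do not change.

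**What to change.** 1. Reword the 5.2.3 lead-in to match the synopsis and 13.5, and use one definition in all three: the number and proportion of ITT subjects with each listed event, regardless of relationship to the device. Show the device-related subset separately, stating which causality levels of Section 11.1.7 define it.
2. In 13.5, restore two rows, one for other adverse events and one for intra- or post-operative complications tied to device deficiencies, each broken down by seriousness and relatedness.
3. Keep the existing row for other serious device-related events as a subset of the restored rows.

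The cost is aligned wording and a few more table rows, with no new data collection because Section 11.1.1 already requires every adverse event to be recorded. The drawback for the sponsor is a fuller, and possibly less favourable, display of other adverse events.
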